10.3.2 Protection Against Risk

10.3.2.1 Confidentiality. To minimize the risk to participant confidentiality, patient identifiers will be removed once his or her data is abstracted and recorded, and only the random study identification number (generated when consent is provided) will be used. All hardcopy study data will be kept in a secured and locked file cabinet. All electronic data will be kept in a password-protected computer database. The only link between patient identifiers and the randomized study identification number will be kept in separate files. Identifiers will never be used in the analysis or presentation of study results.

10.3.2.2 Blood draws. The risks of blood drawing will be minimized by having only experienced medical personnel perform this procedure. The amount of blood that will be drawn falls well within safety standards for blood donation.

10.3.2.3 Questionnaires. Participants may feel uneasy or discomfort in completing the depression, treatment adherence, and physical activity questionnaires. To minimize this risk, questionnaires will be completed in private settings with any questions regarding completion of the questionnaires addressed by trained study team psychology personnel.

10.3.2.4 Nitroglycerin. Brachial artery reactivity testing will be performed in a controlled setting in the Indiana University General Clinical Research Center. To protect against the risks of nitroglycerin administration, registered nurses in the ICRC will monitor the participant's blood pressure throughout brachial reactivity testing. Participants with inherent resting hypotension will be excluded from the NTG-mediated flow dilation portion of the brachial reactivity testing. If the participant becomes symptomatic (e.g. dizzy, perspiring, weak or nauseated, or if the systolic blood pressure falls below 80mmHg or more than 30mmHg below their baseline systolic blood pressure, the study will be stopped immediately). The patient will be placed in Trendelenburg position and be given fluids through the previously placed IV heparin lock if the blood pressure does not recover spontaneously. If the patient develops a headache, an analgesic will be recommended. In addition, participants with recent use of phosphodiesterase inhibitors (e.g. erectile dysfunction medications) prior to NTG administration or planned use after NTG administration will be excluded with the study visit to be rescheduled. Patients with a history of migraine headaches will also not receive NTG as part of their endothelial function assessments.

10.3.2.5 Suicidal ideation and management. Although not an inherent risk of the study intervention or study procedures, participants for this study are eligible only if they have depression as determined through completion of the PHQ-9 questionnaire. As such, these participants may have suicidal ideation at screening or develop suicidal ideation during the course of the study. We have already put into place a protection protocol for just this event in our previous studies in HIV-uninfected depressed patients (please see Appendix at end of this protocol). If a participant reports having thoughts of being better off dead or of hurting him/herself (i.e., responds with a 1, 2, or 3 to PHQ-9 Item #9 or spontaneously reports suicidal ideation), the visit will be immediately stopped, and the research assistant will interview the participant to complete the Patient Suicidality Form (see Appendix). If the participant answers "no" to all three suicide questions or if the patient answers

“yes” only to Question 3 (previous attempt) and the most recent attempt was ≥ 10 years ago, the visit will proceed as normal, and the completed Patient Suicidality Form will be given to the principal investigator.

If the participant answers “yes” to any of the three questions (for Question #3 the previous attempt must be within the past 10 years), the research assistant will immediately contact the principal investigators. [name] (a clinical psychologist) and [name] (a physician) will review the case as soon as possible, but no later than the same day, to determine the appropriate course of action (e.g., immediately contact the patient’s primary care provider, primary HIV provider, clinical social worker, or care coordinator, consult with clinicians at Midtown Community Mental Health Center, and/or escort the patient to the Crisis Intervention Unit at Eskenazi Health). Additional authorities, including the police, may be contacted if immediate harm is of concern. Participants may be withdrawn from the study.

A letter, both an email and a hard copy version, will also be sent to the potential participant’s primary provider notifying him/her of the situation (see below).

If an enrolled participant reports having thoughts of being better off dead or of hurting him/herself during any telephone calls (e.g., a scheduling call or a call to the study team initiated by the participant), the exact same process as outlined above will be initiated. Please see the Appendix for the full Suicide Management Plan.

10.3.2.6 Adverse event financial management, grading, and reporting. In the event of an adverse event, necessary medical and professional intervention will be provided immediately and billed to the participant’s medical insurance (if available). If the participant does not have insurance, care will be provided via the indigent care program at Eskenazi Health Hospital. Standard procedures for reporting deviations from protocols will be followed; serious adverse events that meet the Indiana University IRB prompt reporting requirements will be reported within 10 business days. All adverse events will be graded using The Division of AIDS Table for Grading Adult Adverse Experiences is located at: <http://roc.s-3.com/members/download/adulttox.pdf>.

10.3.2.7 Data and Safety Monitoring. [name] of the Division of Infectious Diseases, Indiana University will serve as the independent chair and monitor for this trial. She will receive reports at least every six months regarding the progress and participant safety during the trial.

10.3 Potential Benefits of the Proposed Research to the Participants and Others

- Potential benefits to the participants include an evaluation of their cardiovascular and immunologic status. They may also derive short-term benefits from the Beating the Blues depression treatment program, although this is not guaranteed. Finally, the participants may also benefit from knowing that their participation will accrue knowledge that could benefit other HIV-infected patients.
- Although there are no guaranteed clinical benefits from those who are randomized to treatment with Beating the Blues, this program appears quite safe when used in HIV-uninfected participants. The standard of care will not be altered in the control participants. Therefore, the ancillary benefits to the participants in the proposed studies significantly outweigh the minimal risks in this study. Moreover, the proposed research may lead to other prevention and therapeutic studies that would demonstrate how to reduce inflammation and improve endothelial function, which consequently may reduce future cardiovascular events in the HIV-infected population. This would benefit society directly by impacting clinical practice.

10.4 Importance of the Knowledge to be Gained

- The knowledge that will be gained from this study will determine the relationships between HIV, depression, inflammation, and endothelial dysfunction. This would potentially impact the clinical care of HIV-infected patients at risk for cardiovascular disease. Furthermore, prevention and therapeutic strategies

for these highly prevalent diseases can then be formulated, thereby reducing morbidity, mortality, and cost to the patients and society in general.

- Again, the risks to the participants are considered minimal. Even if the results are negative, the results of these investigations will add substantially to our knowledge on the mechanisms underlying inflammation and cardiovascular risk in older, HIV-infected patients with depression. Therefore, the importance of the knowledge gained outweighs the risks to the participants.

10.6 Data and Safety Monitoring Plan

- Progress of these studies, including data monitoring, participant enrollment, protocol deviations, and all SAE, will be reviewed by a panel including the PIs (Drs. [name] and [name]), the study statistician ([name]), and an HIV expert investigator at Indiana University not directly connected with this study ([name] of the Division of Infectious Diseases, Indiana University School of Medicine). Reports, which will include descriptions of all adverse events, will be prepared for review by this panel every 6 months. Any study participant prematurely discontinued due to an adverse event will be reviewed immediately. Standard procedures for reporting deviations from protocols to the Indiana University ICRC, IRB, and NHLBI will be implemented. Serious Adverse Events (SAEs) will also be reported to the IRB within 30 working days and subsequently forwarded to NHLBI as required.

10.7 Inclusion of Women and Minorities

There are no exclusion criteria based on gender, racial category, or ethnicity. Based on our previous cumulative experience and the general HIV-infected population cared for at the study sites at the Indiana University Health Medical Center (Eskenazi Hospital, Methodist Hospital, VA Roudebush Hospital, and Indiana University Health Hospital), it is anticipated that approximately 25% of the study participants will be women.

It is also anticipated that approximately 40% and 10% of the study participants will be black and Hispanic, respectively. American Indians, Alaskan Natives, Asians, Native Hawaiians or Other Pacific Islanders are not expected to be represented in the proposed study population due to extremely low representation of these groups within the Indiana University Health Hospitals HIV outpatient clinics and in Indianapolis in general.

10.8 Inclusion of Children

Subjects over the age of 18 will be eligible for enrollment into the proposed trial in Aim #2; as such, children of ages 18-21 will be included in this Aim. However, participants under age 18 will be excluded to minimize confounding from hormonal fluctuations that are encountered during adolescence on the proposal's endpoints of systemic inflammation, altered coagulation, and endothelial function.

Appendix: Suicide Management Plan

Suicide management plans very similar to the one described below have previously been approved by the Indiana University IRB and were successfully implemented in the two other depression trials conducted by our team (IRB #'s 1105005448 and 1110007119). Those suicide management plans were constructed with input from Eskenazi Midtown Community Mental Health Center leadership ([name], Associate Vice President, and [name]), who concluded that the plans provide a high level of protection while minimizing disruption to usual clinical activities. In the present trial, we will assess suicidal ideation at every study visit, and we are prepared to appropriately handle the situation should one of the enrolled patients exhibit suicidal ideation. Of note, zero enrolled participants in our two prior depression trials have exhibited suicidal ideation during their involvement in the studies, likely because patients exhibiting suicidality were not eligible to be enrolled, as is the case for the present trial.

(a) In-Person Study Visits

Suicidal ideation will be assessed using Item #9 of the PHQ-9 at the Screening Visit and all Main Study Visits (see Section 6.1). If a participant reports having thoughts of being better off dead or of hurting him/herself (i.e., responds with a 1, 2, or 3 to PHQ-9 Item #9 or spontaneously reports suicidal ideation) during the Screening, First Entry, Second Entry, Week 12, or Week 24 Visits, the visit will be immediately stopped, and the study coordinators ([name], [name]) running these visits will interview the participant to complete the Patient Suicidality Form (see below). If this interview is required at one of the Weekly BtB Sessions, the graduate student research assistants will perform this interview, as they will conduct these treatment sessions.

The study coordinators have been trained by [name], a clinical psychologist, in conducting the interview to complete the Patient Suicidality Form and in following this protocol. [name] will also serve as the primary supervisor to these study coordinators when it comes to their tasks related to this suicide management plan. In [name] completed (IRB #'s 1105005448 and 1110007119) and ongoing (IRB # 1411802537) clinical trials, he has trained ResNet research assistants to effectively conduct this interview and provide a high degree of protection to patients.

The graduate student research assistants are doctoral students enrolled full-time in IUPUI's clinical psychology Ph.D. program, which is accredited by the American Psychological Association and of which [name] is a core member. The research assistants have completed graduate coursework in psychological assessment, psychological interventions, psychopathology, and ethics and have acquired supervised clinical experience in local healthcare settings. The graduate student research assistants have also been trained by [name] in conducting the interview to complete the Patient Suicidality Form and in following this protocol. [name] is also the primary supervisor of graduate student research assistants.

It is worth noting that neither the study coordinators nor the graduate student research assistants will be making any decisions regarding how to handle a situation. Instead, they will collect information by administering a highly structured, 3-question interview (Patient Suicidality Form, found below) and will follow the straightforward, step-by-step protocol described in the next paragraph. They will be instructed to call [name] if they are unsure about a participant's response to any of the three questions. As he has done in his past depression trials and is described above, [name] will train the study coordinators and the graduate student research assistants in administering the brief interview and in following the protocol. This training will be repeated periodically during the study period.

If the participant answers “no” to all three suicide questions or if the patient answers “yes” only to Question 3 (previous attempt) and the most recent attempt was ≥ 10 years ago, the visit will proceed as planned, and the completed Patient Suicidality Form will be given to [name].

If the participant answers “yes” to any of the three questions (for Question #3 the previous attempt must be within the past 10 years), the study coordinators or the graduate student research assistant will immediately stop the visit, will contact Drs. [name] and/or [name], and will stay with the participant until a decision is made. If clinically indicated (e.g., the situation is an emergency), a graduate student research assistant and/or [name] will go to the visit location (Infectious Diseases Research Clinic or ICRC) to assist the study coordinators.

Drs. [name] and/or [name] will review all cases screening positive for suicidal ideation immediately to determine the appropriate course of action – e.g., interview the patient to obtain further information, immediately contact the patient’s HIV provider or clinical social worker to involve them in the decision-making process, consult with clinicians at the Eskenazi Health Midtown Community Mental Health Center to aid in the decision-making process, escort the patient to the Eskenazi Health Crisis Intervention Unit (‘warm handoff’), and/or contact the police if the patient is at imminent danger of harm and is refusing all care. Either [name] or [name] will also call the participant’s HIV provider notifying him/her of the situation if the provider was not involved in the decision-making process. Regardless of the exact course of action, the study team will ensure that the participant is connected to the appropriate existing clinical services. If the patient’s HIV provider no longer believes that the patient is appropriate for this trial following this situation, the patient will be withdrawn from the trial.

Of note, because patients exhibiting active suicidal ideation are not eligible for this trial, we expect that it will be a rare occurrence that an enrolled patient will screen positive for suicidal ideation. Zero enrolled participants in our two prior depression trials have exhibited suicidal ideation during their involvement in the studies.

(b) Study Telephone Contacts

If a participant reports having thoughts of being better off dead or of hurting him/herself (i.e., responds with a 1, 2, or 3 to PHQ-9 Item #9 or spontaneously reports suicidal ideation) during a study call (e.g., the start or end of a remote BtB session, a scheduling call, or a call to the study team initiated by the participant), the study coordinator or a graduate student research assistant will interview the participant to complete the Patient Suicidality Form (found below).

If the potential participant answers “no” to all three suicide questions, the call will proceed as planned and the completed Patient Suicidality Form will be given to [name]. If the participant answers “yes” to any of the three questions (for Question #3 the previous attempt must be within the past 10 years), the study coordinator or a graduate student research assistant will immediately contact Drs. [name] and/or [name]. Drs. [name] and/or [name] will review the case immediately to determine the appropriate course of action – e.g., interview the patient to obtain further information, immediately contact the patient’s HIV provider or clinical social worker to involve them in the decision-making process, consult with clinicians at the Eskenazi Health Midtown Community Mental Health Center to aid in the decision-making process, escort the patient to the Eskenazi Health Crisis Intervention Unit, and/or contact the police if the patient is at imminent danger of harm and is refusing all care. If a participant prematurely terminates a call after reporting suicidal ideation, the study coordinator or a graduate student research assistant will immediately contact Drs. [name] and/or [name]. Once again, Drs. [name] and/or [name] will review the case immediately to determine the appropriate course of action. Either [name] or [name] will also call the participant’s HIV provider notifying him/her of the situation if the provider was not involved in the decision-making process. Regardless of the exact course of action, the study team will ensure that the participant is connected to the appropriate existing clinical services.

If the patient's HIV provider no longer believes that the patient is appropriate for this trial following a situation, the patient will be withdrawn from the trial.

It should be noted that the informed consent form for this trial contains a section describing the steps that will be taken if an enrolled participant reports suicidal ideation on a questionnaire or spontaneously.

Patient Suicidality Form (administered verbally by the research assistant)

CONFIDENTIAL

Research Assistant: _____ Date: _____

Patient's Name: _____ Hospital ID: _____

Patient's Address: _____

Patient's Phone Number: _____ Patient's PCP: _____

I'm going to ask you a few questions that are part of this study, because we have seen that in some patients with these symptoms, these are important concerns.

1. Do you have a suicide plan? Yes _____ No _____

Comments:

2. Have you been struggling against thoughts about committing suicide? Yes _____ No _____

Comments:

3. Have you attempted suicide in the past? Yes _____ No _____

If YES, in what year was the most recent attempt? _____

Comments:

If the participant answers “yes” to any of the three questions (for Question #3 the previous attempt must be within the past 10 years), you must carefully follow the procedures described in the Suicidal Ideation Protection Protocol.

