3.4 Beating the Blues Treatment Sessions and Usual Care

3.4.1 Beating the Blues

To minimize treatment barriers, attrition, and subject burden, the BtB treatment sessions will occur in private at [name] laboratory, the ICRC, the Infectious Diseases Research Clinic at Eskenazi Health Hospital, or a location selected by the patient where s/he can access a computer with internet, such as the patient's home, the patient's work, a family member's/friend's home, or a public library. The location will be chosen by the participant. To help maintain privacy, patients will be provided with ear bud headphones if they plan to complete BtB sessions at remote locations and do not already own a pair of headphones that they would rather use. We will also tell patients that, if they choose to complete BtB session where others are present, these other people (e.g., family member or friend) may realize that they are completing a treatment for depression. It will be up to each patient to decide if the available remote locations provide sufficient privacy. Up to 8 sessions will be performed between the Second Entry Visit and the Week 12 Visit. The PHQ-9 questionnaire will be administered at each of the Weekly BtB Sessions. No physiologic or biologic assessments will be performed during these sessions. The participants need not be fasting for these sessions.

At each in-person BtB session, a research assistant trained in the use of this intervention will first collect homework and will start the appropriate session on a computer. The patient will then work through the session alone at his/her own pace. At the end of the session, the research assistant will give the patient the printed homework assignment and will schedule the next session.

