Remote BtB sessions will be scheduled, just like in-person sessions. Patients who select the remote treatment option will complete the first BtB session in person, at which time they will be given a BtB binder with printouts of all future homeworks. To begin each remote BtB session, an assistant will call the patient to instruct the patient to put last week's homework in the BtB binder, to address any technical issues, and to ensure that the patient has launched the correct BtB session for that day. The patient will then work alone through the BtB session at his/her own pace, with the assistant monitoring progress remotely on the secure BtB website set up for this trial. To end the session, the assistant will call the patient back to address any questions and ensure that the patient has identified the correct printed homework in the BtB binder.

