5.0 STUDY TREATMENT

5.1 Beating the Blues

To minimize treatment barriers, attrition, and subject burden, the BtB treatment sessions will occur in private at [name] laboratory, the ICRC, the Infectious Diseases Research Clinic at Eskenazi Health Hospital, or a remote location selected by the patient where s/he can access a computer with internet, such as the patient's home, the patient's work, a family member's/friend's home, or a public library. The location will be chosen by the participant. Patients will be provided with ear bud headphones if they plan to use them at remote locations and do not already own a pair of headphones that they would rather use. Up to 8 sessions will be performed between the Second Entry Visit and the Week 12 Visit. The PHQ-9 questionnaire will be administered at each of the Weekly BtB Sessions. No physiologic or biologic assessments will be performed during these sessions. The participants need not be fasting for these sessions.

At each in-person BtB session, a psychology research assistant trained in the use of this intervention will first collect homework and will start the appropriate session on a computer. The patient will then work through the session alone at his/her own pace. At the end of the session, the research assistant will give the patient the printed homework assignment and will schedule the next session.

Remote BtB sessions will be scheduled, just like in-person sessions. Patients who select the remote treatment option will be given a BtB binder with printouts of all future homeworks at the time of randomization (i.e., the end of the Second Entry Visit). To begin each remote BtB session, an assistant will call the patient to instruct the patient to put last week's homework in the BtB binder, to address any technical issues, and to ensure that the patient has launched the correct BtB session for that day. The patient will then work alone through the BtB session at his/her own pace, with the assistant monitoring progress remotely on the secure BtB website set

up for this trial. To end the session, the assistant will call the patient back to address any questions and ensure that the patient has identified the correct printed homework in the BtB binder.

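### The protocol foresees a call cut off after reported suicidal ideation and allows sessions away from home, but no step records where the participant is

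*Combined protocol and SAP*

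**What the plan says.** Section 3.4.1 lets a participant do sessions at "a location selected by the patient where s/he can access a computer with internet", giving home, work, the home of family or friends, and a public library as examples. Section 5.1 repeats this ("a remote location selected by the patient where s/he can access a computer with internet"). On assessment, 3.4.1 states: "The PHQ-9 questionnaire will be administered at each of the Weekly BtB Sessions". Section 5.1 agrees.

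Remote sessions are supported by two calls. The opening call deals with last week's homework and is also meant "to address any technical issues, and to ensure that the patient has launched the correct BtB session for that day". The closing call deals with questions and the next homework. Section 3.4.1 adds: "Remote BtB sessions will be scheduled, just like in-person sessions". It also says that participants who choose the remote option "will complete the first BtB session in person", and that privacy at remote places is discussed with them.

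Part (b) of the Appendix covers ideation reported on study calls and names the start and end of a remote session among them. It then deals with the cut-off call: "If a participant prematurely terminates a call after reporting suicidal ideation", staff contact the principal investigators immediately, and they review the case immediately. The actions listed for telephone reports include a further interview with the patient, involving the HIV provider or social worker, consulting the mental health centre, escort to the crisis unit, and calling the police when danger is imminent and all care is refused. The HIV provider is telephoned if not already involved. The team must see that the participant is linked to clinical services whatever course is chosen.

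**The concern.** At an in-person visit the participant's whereabouts are known, because part (a) of the Appendix has staff remain with the participant while the investigators decide. A telephone call that has ended has no equivalent. If the participant is at a library or a friend's home, hangs up after a positive answer and does not pick up again, the location can no longer be obtained from them. The plan's police option then has, at best, an address on file that may be the wrong place. The matter is participant safety. The FMD endpoint, the sample size and the analysis are not affected.

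**Working it through.** No figure in the plan needs reproducing. The check sets the relevant texts side by side.

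| Place in the protocol | What it provides | Records current location? |
|---|---|---|
| 3.4.1 and 5.1, opening call | Homework, technical issues, correct session launched | No |
| 3.4.1 and 5.1, closing call | Questions, correct homework | No |
| 3.4.1, scheduling and privacy advice | Staff may learn the planned setting | Not recorded or confirmed on the day |
| 7.0 and 10.3.2.5, telephone reports | Same procedure as at visits | No |
| Appendix (b), cut-off call | Immediate contact with and review by the investigators | No |
| Patient Suicidality Form, header | Name, hospital ID, address, phone, PCP | Address not labelled as current location |
| Patient Suicidality Form, Questions 1 to 3 | Plan, struggling against thoughts, past attempts | No |

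The form is completed in an interview that begins after ideation has been reported. A caller who hangs up at once may never be asked anything on it.

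**How narrow the gap is.** The missing step matters only if all of these hold: the session or call is taken remotely; the participant is not at the address on file; ideation is reported; the participant ends the call; re-contact fails; and the investigators judge that someone must be sent. The documents give no probability for any link in this chain, so no rate can be calculated. Two facts point to rarity. Active suicidality is an exclusion (4.2.3), and the Appendix reports no ideation among enrolled participants in two earlier trials. Neither rules the event out. Under 4.2.3 a person with a positive Item 9 who answers no to all three form questions can still enrol, and the documents do not say whether the earlier trials used remote sessions.

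**Workload of the fix (not a measure of risk).** Inputs: 55 participants in the intervention arm, up to 8 sessions each, and 7 remote at most if the first is in person as 3.4.1 says (5.1 does not repeat that condition). Assumption: 10 to 30 seconds to take location and call-back number at the opening call.

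- Maximum remote sessions: 55 × 7 = 385, or 55 × 8 = 440.
- Opening call, low: 385 × 10 s = 3,850 s, about 64 min (1.1 h) over the whole trial.
- Opening call, high: 440 × 30 s = 13,200 s = 220 min (3.7 h).
- If reconfirming at the closing call took as long again, the high figure would double: 440 × 60 s = 26,400 s = 440 min (7.3 h).
- Per participant, high: 8 × 60 s = 480 s = 8 min across all sessions.

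These totals assume that every session that can be remote is remote, so they are ceilings.

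**The case against.** The sponsor has a fair reply on several counts.

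- **The call descriptions are not full scripts.** They do not mention the PHQ-9 either, although it is required at each session. Silence in 3.4.1 and 5.1 therefore does not show that staff never ask where someone is. This stands, and it limits the point to what the protocol text requires. Call scripts and training material are not in the documents. The consent form, which the Appendix says describes the steps taken, was not available for review.
- **The plan already responds to a cut-off call.** A reader might infer that nothing happens after a hang-up. The text does not support that. Immediate review, possible re-contact, the HIV provider call and the duty to connect the participant to services all apply. None of them supplies a current location if re-contact fails.
- **Staff are free to note location.** A reader might take the Appendix's statement that "they will collect information by administering a highly structured, 3-question interview" as barring other questions. It does not. The sentence sits in part (a), explains that these staff make no management decisions, and says nothing against a further note. The form has a comments space after each question. Being free to note location is still not a step that asks for it.
- **Escort is hardly affected.** It normally involves a participant who has been reached and can say where they are. This also stands, so the practical gap is mainly police dispatch.
- **The event is rare.** Agreed, and no rate is claimed.

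**Conclusion.** The point holds as a statement about the protocol text. Sessions away from home are allowed, a call ended after reported ideation is foreseen, and no supplied step records where the participant then is. The consequence is confined to a participant who is away from the address on file, hangs up and cannot be reached again. In that case the plan's own police option lacks a current place to go. A reader might go further and conclude that remote participants are unprotected or that staff do not know where they are. The documents do not support either: several safeguards remain, and scheduling may tell staff the planned setting.

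The frequency is unknown and expected to be low. The conclusion assumes that unseen scripts, training or consent text do not already contain the step. If they do, the amendment only brings the protocol into line with practice. A minor amendment is justified because the possible harm is serious, the information cannot be recovered from the participant once contact is lost, and the cost is very small.

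**What to change.** 1. In 3.4.1 and 5.1, have the assistant record the participant's current location and a call-back number at the opening call of each remote session, before the PHQ-9 is given, and briefly reconfirm location at the closing call.
2. Add a 'location now' line to the Patient Suicidality Form for other study calls. Leave its timing to the interviewer, since a badly timed question could unsettle a caller. This is partial protection: someone who hangs up at once is still not located.
3. In the cut-off-call step of Appendix (b), state that any recorded location and number go to the principal investigators. Leave call-back and all other action to their judgement, as the plan does now.

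The cost is a few seconds per call (at most about 8 minutes per participant under the assumptions above), a minor protocol and form amendment, and a training update that fits the periodic retraining the Appendix already plans. The privacy burden is small but real, because workplaces or friends' addresses would be noted repeatedly for people in an HIV trial. Location notes should stay with the identifiers, which 9.15 keeps in a locked file, and out of the study database.
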